16.4 Study Sample Size, Decision Rule, and Study Duration

16.41 *Sample size:* This study requires 153 evaluable women for the primary endpoint analysis. We anticipate accruing 15 additional patients to account for ineligibility, cancellation, major treatment violation, or other reasons. The maximum projected accrual is therefore 168 women, and we expect a maximum of 60 and a minimum of 40 women within each cohort (photon, proton, and brachytherapy).

16.42 *Study Decision Rule and Operating Characteristics:* Olivotto et al. previously reported interim cosmetic and toxicity results from a randomized trial comparing APBI using 3D-CRT versus WBI. In this study, the same 3DCRT dose and fractionation was used as in the previously discussed NSABP B-39/RTOG 0413 randomized controlled trial comparing 3DCRT or brachytherapy APBI with WBI. At 3 years, the percentage difference in patients with adverse cosmesis in the APBI arm compared to baseline by trained nursing assessment was 10.6%. The proposed analysis is to compute the percentage difference in patients with adverse cosmesis (fair or poor cosmesis) at 3 years compared to baseline. A one-sided 95% confidence interval (with the upper bound of the interval) was computed, by assuming the difference in adverse cosmesis rate at 3 years compared to baseline is 10%, and the distance from 10% to the upper bound of the CI is 4%. The decision rule would be of the following:

- If the upper bound of the one-sided CI for the difference of adverse cosmesis rate lies above 14%, then recommend no further investigation and conclude that there is no sufficient evidence to accept the adverse cosmesis rate of 3 fraction accelerated APBI.
- If the upper bound of the one-sided CI for the difference of adverse cosmesis rate lies below 14%, then recommend further investigation and conclude the increase in 3-year adverse cosmesis rate of 3 fraction accelerated APBI is potentially acceptable.

The study operating characteristics is determined as the chance of declaring that APBI warrants further study, assuming a true value for the difference in adverse cosmesis rate at 3 years compared to baseline for APBI. The table below shows the operating characteristics of this trial with 153 patients and the decision rule given above.

True increase in adverse cosmesis rate at 3 years compared to baseline	Probability of concluding PBI warrants further study
5%	98.4%
10%	72.8%
15%	48.6%
20%	29.8%

If the increase in APBI adverse cosmesis rate from baseline is 5.0%, there is a 98.4% chance of concluding that the APBI adverse cosmesis increase from baseline is acceptable; this drops to 72.8% if the true rate is 10%, and further drops to 49.6% if the true rate is 15%. If the increase in APBI adverse cosmesis rate from baseline at 3 years is 20% or greater, we are most likely to recommend no further investigations, and conclude that the increase in APBI adverse cosmesis rate is unacceptably high.

Other considerations: Adverse events, quality/duration of response, and patterns of treatment failure observed in this study, as well as scientific discoveries or changes in standard care will be taken into account in any decision to terminate the study.

16.43 Preliminary Analysis: The preliminary analysis is to examine whether the data from the three methods (photon, proton and brachytherapy PBI) can be combined by assessing any difference in the safety profile and baseline patient and tumor characteristics. We will conclude that the variability in the three samples is acceptable and proceed to the primary analysis if all the following conditions are met:

- The difference in rate of grade 3 toxicity between the groups is $\leq 10\%$.
- There is not a significant difference in the rate of IBTR between the groups (using pair-wise chi-squared tests with Bonferroni correction for multiple comparisons).
- The distribution of African Americans and the percentage of cytotoxic chemotherapy use between the groups is not significantly different (using pair-wise chi-squared tests with Bonferroni correction for multiple comparisons).
- The distribution of age between the groups is not significantly different (p -value ≥ 0.05 using a Tukey's test). The difference in age in 10 increments (50-59, 60-69, and ≤ 70) will be reported.
- Tumor size will be dichotomized to two categories ($\leq 1\text{cm}$ vs $1\text{-}2\text{cm}$). The percentage of larger tumor ($1\text{-}2\text{cm}$) between the groups is not significantly different (using pair-wise chi-squared tests with Bonferroni correction).

If any of the above conditions are failed to be met, we will only report the safety and efficacy of each individual arm as secondary and exploratory endpoints.

16.44 Accrual time and Study duration: Since 10/1/2012 patients have been treated with brachytherapy APBI using an 8 or 10 fraction regimen and prospectively followed as part of a clinical registry at the Mayo Clinic in Rochester, MN. Patient interest in the procedure has steadily increased, and in the last 3 months, 13 patients have been treated (median 4.3 patients per month), all of whom would be eligible for this study. A similar to increased level of accrual of brachytherapy patients is anticipated during the course of this study as familiarity with this procedure amongst surgical and radiation oncology providers rises. With the addition of the photon APBI alternative for patients, we anticipate an accrual rate of 5 patients per month for the first year until the opening of

the Mayo proton facility, after which an accrual of 8 patients per month is anticipated. Therefore, the accrual period for this study is expected to be approximately 3 years. We plan to open this study at the Mayo Clinic in Scottsdale and Jacksonville which will further enhance accrual. Final analysis may begin approximately 5 years after the trial begins, i.e. as soon as the last patient registered has been observed for at least 24 months. A maximum of 60 patients and a minimum of 40 patients will be enrolled per treatment arm.

16.5 **Primary Analysis:** The primary analysis will be to estimate the percentage difference in patients with adverse cosmesis (fair or poor cosmesis) at 3 years compared to baseline. All patients meeting the eligibility criteria who have signed a consent form and started treatment will be in the primary analysis. The percentage difference in patients with adverse cosmesis will be estimated using a binomial estimator (number of women who had an adverse cosmesis event at 3 years minus number of women who had an adverse cosmesis event at baseline, and then divided by total number of women in the primary analysis) and a 95% exact binomial confidence interval. As mentioned above, the following decisions will be made based on the 95% CI:

- ***The upper bound of the 95% CI lies below 14%:*** APBI adverse cosmesis is acceptable.
- ***The upper bound of the 95% CI lies above 14%:*** No evidence to show that APBI adverse cosmesis is acceptable.

16.6 **Secondary Analyses**

16.61 *Acute adverse events (up to 90 days post-RT):* All patients who were registered to the study and started treatment will be included in the acute adverse event analysis. An acute adverse event is an AE, regardless of attribution, that occurs up to 90 days post-RT. The maximum grade for each type of acute AE will be recorded for each patient. Data will be summarized as frequencies and relative frequencies. Additionally, the relationship of the adverse event(s) to the study treatment will be taken into consideration.

16.62 *Late adverse events:* All patients who were registered to the study and started treatment will be included in the late adverse event analysis. A late adverse event is an AE, regardless of attribution, that occurs at least 90 days post-RT and up to 3 years post-RT. The maximum grade for each type of late AE will be recorded for each patient. Data will be summarized as frequencies and relative frequencies. Additionally, the relationship of the adverse event(s) to the study treatment will be taken into consideration. Prior APBI reports have suggested rates of grade 3 or 4 toxicity to be $\leq 10\%$.^{18,47,55,56}

16.63 *Quality of life:* The QOL measurements will be summarized at each time point as mean \pm SD and median (minimum value, maximum value). Changes in the QOL measurements from baseline will be determined at each follow-up measurement. These will be displayed as spaghetti plots. The assessment of the changes at each time point will be done with a paired t-test or Wilcoxon signed rank test, whichever is appropriate.

16.64 *Cosmesis*: The values of the cosmesis instruments (patient self-reported and panel-assessed) will be summarized with the frequencies of fair or poor cosmesis events at baseline and 3 years, and the difference at 3 years, as well as their relative exact binomial confidence intervals.

16.65 *IBTR incidence*: The IBTR cumulative incidence will be estimated using a competing risks method (Gooley et al.). The competing risks will be regional/distant breast cancer recurrence and death.

16.66 *Regional recurrence incidence*: The regional breast cancer recurrence cumulative incidence will be estimated using a competing risks method (Gooley et al.). The competing risks will be local/distant breast cancer recurrence and death.

16.67 *Distant recurrence incidence*: The distant breast cancer recurrence cumulative incidence will be estimated using a competing risks method (Gooley et al.). The competing risks will be local/regional breast cancer recurrence and death.

16.68 *Disease-free survival*: DFS is defined as the time from registration until the time of disease recurrence or death due to any cause. The DFS will be estimated with a Kaplan-Meier estimator and curve. Estimates will be given for specific time points along with 95% CIs.

16.69 *Overall survival*: The OS will be estimated with a Kaplan-Meier estimator and curve. Estimates will be given for specific time points along with 95% CIs.

16.7 Exploratory Analyses: Exploratory comparisons of the local control, acute and late adverse events, quality of life, and cosmesis among the three radiation regimens will be made. Comparisons of categorical variables will be done with a chi-square test or Fisher's exact test, whichever is appropriate. Comparisons of continuous variables will be done with an ANOVA or Kruskal-Wallis test, whichever is appropriate. Measurements over time (i.e. QOL) will be summarized as area under the curve (AUC) and these values will be analyzed as continuous outcomes. All tests will be two-sided and a p-value less than 0.05 will be considered significant. No adjustments will be made for multiple comparisons.

Correlative Science: Adverse cosmesis has been reported to be significantly increased in prior studies of APBI, yet predictors of adverse cosmesis are poorly understood.^{47,48} If a subset of patients at high risk of complications could be identified, their treatment could be personalized or they could be counseled to pursue other therapeutic options altogether. In the setting of WBI, factors previously reported to be associated with worsened cosmesis include inferior tumor location, large excision volume, the presence of postoperative breast complications, higher dose (including radiotherapy boost), inhomogeneity, and use of concurrent chemotherapy.⁵⁷⁻⁵⁹ In order to begin identifying predictive factors for fair and poor cosmesis following 3 fraction APBI we will analyze clinical and dose volume parameters correlated with increased risk.

It is generally believed that clinical and dose-volume factors alone are not sufficient to explain the patient to patient variation in late toxicity following a course of radiation therapy.^{60,61} Indeed, patient specific histologic and genomic features may also be of significant importance in determining variation in normal tissue radiation response and risk of adverse cosmesis. There is considerable variation in sensitivity to radiation across tissue type.⁶² Therefore, as a preliminary step in considering biomarkers of risk of adverse cosmesis, we will analyze non-cancerous breast tissue from the lumpectomy specimen. In particular, we will determine whether the ratio of fat, connective tissue, and epithelium of the normal breast tissue away from the tumor is predictive of adverse cosmesis following APBI. A number of studies have correlated breast histopathological findings with mammography.⁶³⁻⁶⁵ Mammographic density is largely determined by the relative amount of fat, connective tissue, and epithelium. If a correlation is made between histologic make-up of the normal breast parenchyma and adverse cosmesis, we will explore whether patients can also be stratified based on preoperative mammographic density, as determined by the qualitative Breast Imaging Reporting and Data System (BI-RADS) method for density assessment developed by the American College of Radiology.

Cytokines and growth factors are involved in the radiation response and tissue remodelling and may serve as predictive factors for normal tissue damage. For example, levels of transforming growth factor β 1 (TGF- β 1) vary substantially between individuals and has previously been associated with radiation fibrosis in early-stage breast cancer patients.⁶⁶ TGF- β 1 is a multi-functional cytokine that attracts fibroblasts and stimulates collagen production.⁶⁷ Although basal levels may be important, expression levels of this protein are induced within an hour or less after exposure to ionizing radiation and therefore TGF- β 1 induction following radiation may be a better functional marker of an elevated fibrotic response.^{68,69} Therefore, blood will be drawn pre-treatment and on the last day of radiotherapy 1 hour following the final fraction. The pre and post radiotherapy levels of TGF- β 1 and other proteins in the fibrotic response will be compared and association with adverse cosmesis following APBI will be determined.

Mounting evidence also suggests that genetic variation may play an important role in determining susceptibility to radiation toxicity.⁷⁰ Radiogenomics is an emerging field aimed at studying genetic differences associated with variability in the effectiveness and toxicity of radiation.⁶¹ We plan to use a candidate gene approach⁶¹ to investigate the association of single nucleotide polymorphisms (SNPs), previously correlated with radiation normal tissue toxicity, with adverse cosmesis following 3 fraction APBI. For example, in addition to TGF- β 1, SNPs in the XRCC1 (codon 241) and XRCC1 (codon 399) genes, the protein products of which function in the DNA repair pathways of based excision repair and homologous recombination, respectively, have been correlated with increased risk of subcutaneous fibrosis following breast cancer radiotherapy. [REDACTED]

[REDACTED] laboratory at the Mayo Clinic has used a genome-wide association approach in human lymphoblastoid cell lines to identify radiation response biomarkers. C13orf34, MAD2L1, PLK4, TPD52, and DEPDC1B were identified and functionally validated as modifiers of radiation response. These promising findings, however, require further clinical validation.^{61,71}

The final design of these future genomic and proteomic studies will depend on the event rate observed in the trial, cost and state of technology at the time of per protocol cosmetic evaluation of all patients enrolled. They may occur as part of a meta-analyses of patients treated with hypofractionated breast cancer radiotherapy from other institutions.

Over Accrual: If more than the target number of patients are accrued, the additional patients will not be used to evaluate the stopping rule or used in any decision making processes; however, they will be included in final endpoint estimates and confidence intervals.

16.8 Results Reporting on ClinicalTrials.gov: At study activation, this study will have been registered within the “ClinicalTrials.gov” website. The Primary and Secondary Endpoints along with other required information for this study will be reported on ClinicalTrials.gov. For purposes of timing of the Results Reporting, the initial estimated completion date for the Primary Endpoint of this study is 5 years after the study opens to accrual. The definition of “Primary Endpoint Completion Date” (PECD) for this study is at the time the last patient registered has been followed for at least 3 years.

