prescribed in NSABP B-39/RTOG 0413 as well as the Canadian Accelerated Partial Breast Irradiation Using Three-Dimensional Conformal External Beam Radiation Therapy (RAPID) randomized trials. Olivotto et al. recently reported the interim cosmetic and toxicity results from the latter study which compared 3D-conformal APBI to whole breast irradiation (WBI). 82% of patients in the WBI arm received 42.5Gy in 16 fractions, and just 21% of patients received a boost. At 3 years, 29% of patients in the APBI arm had fair or poor cosmesis compared to 19% at baseline, an absolute difference of 10%. In the WBI arm, the rate of fair or poor cosmesis at 3 years was 17%, the same rate as at baseline. Telangiectasia and breast induration were also significantly more common with external beam APBI ($p<0.001$), as was fat necrosis ($p=0.01$).⁴⁷ Other institutions have also noted adverse toxicity with similar regimens.^{22,48}

There are likely several reasons for the higher than expected adverse cosmesis seen in the RAPID trial that may be also relevant to the increased complications seen with brachytherapy in population based analyses. These considerations have been taken into account in the development of the brachytherapy, external beam photon and proton fractionation regimens of this study. First, the dose of 38.5Gy in 10 fractions given twice daily was too high. The RAPID trial investigators recognized that this prescription had a higher biologic equivalence than the whole breast regimens used in the study, but they hypothesized that the reduced volume of APBI would make up for this difference. Indeed, using an α/β ratio of 3.5 for late effects, the 3.85Gy x 10 fraction regimen translates into 51.5Gy in 2 Gy fractions, higher than the 2Gy fraction equivalent dose of 42.5Gy delivered in 16 fractions (47.7Gy₂) which was received by the majority of patients in the WBI control arm of the study.

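### The 4-point precision behind N=153 and the 14% limit holds for a normal-approximation interval with no improvers, not for the exact interval on a before-after difference named in 16.5

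*Combined protocol and SAP*

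**What the plan says.** Section 16.41 fixes the size: "This study requires 153 evaluable women for the primary endpoint analysis". Section 16.42 gives the basis: "A one-sided 95% confidence interval (with the upper bound of the interval) was computed", for an assumed increase that "is 10%, and the distance from 10% to the upper bound of the CI is 4" percentage points. That sum gives the decision limit: "If the upper bound of the one-sided CI for the difference of adverse cosmesis rate lies above 14%, then recommend no further investigation"; a bound below 14% leads to further investigation. The same section states a 72.8% chance of a favourable conclusion if the true increase is 10%.

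Section 16.5 defines the primary estimate as the number of women with adverse cosmesis at 3 years, minus the number at baseline, divided by all women analysed. To this it attaches "and a 95% exact binomial confidence interval", and it compares the upper bound with 14%. It refers back to the earlier rule but does not itself say whether the interval is one-sided or two-sided.

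The documents name no sample-size formula, and they give no assumption about how many women move from adverse to non-adverse cosmesis. They also do not say how an exact binomial interval is to be formed for a net difference.

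**The concern.** The 14% limit is the planning value plus the planned precision, so a trial that observes about its planning value should land at the limit. That works only if the interval used at analysis has the width assumed at design. The design figures appear to rest on a normal approximation for one proportion, whereas the analysis names an exact interval and the endpoint is a change within each woman. Both differences widen the interval. At stake is the go/no-go recommendation: a reader of 16.42 would expect an observed increase of about 10% to be borderline, and would take the stated precision and passing probabilities as properties of the analysis in 16.5.

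**Working it through.** **Inputs.** n = 153 (16.41); one-sided 95%, so z = 1.645; assumed difference d = 10%; distance 4 points; limit 14% (all 16.42); exact binomial interval on the net difference (16.5). The share of women who improve from adverse to non-adverse, r, is not in the documents and is an assumption throughout.

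**1. Reproducing N.** The single-proportion normal-approximation (Wald) precision formula is n = z² p(1−p)/h². With p = 0.10 and h = 0.04:

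1.645² × 0.10 × 0.90 / 0.04² = 152.2, rounded up to 153.

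The half-width at n = 153 is 3.99 points. With z = 1.96 the formula gives 216.1, so the two-sided version does not fit.

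**2. The interval named in 16.5, with the net count treated as binomial.** These are Clopper-Pearson upper bounds at n = 153, with the Wald bound for comparison.

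| Net count | Increase | Exact, one-sided 95% | Exact, two-sided 95% | Wald, one-sided 95% |
|---|---|---|---|---|
| 12 | 7.84% | 12.40% | 13.30% | 11.42% |
| 14 | 9.15% | 13.93% | 14.88% | 12.98% |
| 15 | 9.80% | 14.69% | 15.65% | 13.76% |
| 16 | 10.46% | 15.45% | 16.43% | 14.53% |

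At 15/153 the one-sided distance is 14.69 − 9.80 = 4.9 points. The largest net count with a bound below 14% is 14 (exact one-sided), 12 (exact two-sided; 13 gives 14.09%) or 15 (Wald one-sided).

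**3. A paired difference.** Let b be the share who worsen and r the share who improve, so d = b − r. The variance of the estimate is (b + r − d²)/n = (d(1−d) + 2r)/n, and the one-sided distance is 1.645 × √[(d(1−d) + 2r)/153]. At d = 0.10:

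| Improvers r (assumed) | d(1−d) + 2r | Distance | Upper bound |
|---|---|---|---|
| 0% | 0.09 | 4.0 points | 13.99% |
| 2% | 0.13 | 4.8 points | 14.8% |
| 5% | 0.19 | 5.8 points | 15.8% |
| 13.5% | 0.36 | 8.0 points | 18.0% |

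The last row is an extreme. It treats a woman's baseline and 3-year ratings as independent at the rates that section 1.3.2 reports for the comparison trial ("29% of patients in the APBI arm had fair or poor cosmesis compared to 19% at baseline"): 0.19 × 0.71 = 0.135.

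**4. Chance of passing at a true 10% increase.**

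- Exact one-sided rule, no improvers: P(X ≤ 14) for Binomial(153, 0.10) = 42.8%.
- Exact two-sided rule, no improvers: P(X ≤ 12) = 23.0%.
- Paired Wald one-sided rule: with no improvers, P(X ≤ 15) = 53.6%. From multinomial counts it is 40.4% with 2% improvers and 31.9% with 5%.

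Section 16.42 states 72.8%.

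**The case against.** The best defence is that planning with a normal approximation and analysing with an exact interval is common, and that here the two rules differ by one woman: 15 allowed against 14. This stands as a measure of the exact-versus-Wald gap on its own (one-sided, no improvers). N = 153 also follows from the stated inputs, so it is not an arithmetic error. A reader might infer that the trial is too small, but nothing in the documents requires a 4-point distance for its own sake.

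It is also fair that the 4 points are delivered in one case, a Wald interval with r = 0, where the bound at 10% is 13.99%. The wider paired distances depend on improver rates that the documents do not give.

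A reader might say that a trial observing exactly 10% would be told to stop. That result cannot occur, since 10% of 153 is 15.3 women. Of the attainable neighbours, 16 fails under both intervals, and only 15 changes from pass to fail when the exact one-sided interval replaces the Wald one.

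A reader might also blame the 72.8% on the change of interval. The figures do not support this, because the Wald rule itself gives at most 53.6%; the table has a separate problem. Nor is the stated 98.4% at a true 5% increase shown to be wrong. The exact one-sided rule gives 99.0% with no improvers and about 96.6% with 2%, and 98.4% lies between them.

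What the defence does not answer is that 16.42 states a precision and a passing probability for a rule that 16.5 then applies with a different interval, on an endpoint with a different variance.

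**Conclusion.** The concern holds as a mismatch between the design figures and the stated analysis. Under 16.5, with the net count read as binomial, the distance near the planning value is 4.9 points one-sided (5.8 or 5.9 two-sided, from 15.65 − 9.80 = 5.85), not 4. A net 15/153 fails on either sidedness. With an interval suited to paired data the distance grows with the share of improvers, and 4 points is the value at zero improvers. Neither interval reproduces the stated 72.8%.

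Three things are inferred or assumed: that the Wald formula produced 153 (it matches, but is not named), that Clopper-Pearson on the net count is what 16.5 intends, and the values of r. The second reading is generous to the plan, because a net difference can be negative, is not a binomial count, and is more variable once some women improve. The finding does not show that N or the 14% limit must change. It should be corrected because the recommendation for or against further study rests on these figures.

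**What to change.** Keep N = 153 and the 14% limit, and make the changes in this order.

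1. In 16.5, name one interval suited to a paired difference and state that its bound is one-sided 95%, as in 16.42.
2. In 16.42, replace the 4-point statement with the precision of that interval at n = 153 over a stated range of improver rates. For a paired Wald bound at d = 10% this is 4.0, 4.8 and 5.8 points at 0%, 2% and 5%, with 8.0 points at 13.5% as the independence extreme.
3. Recompute the passing probabilities from the same rule. At a true 10% increase, the paired Wald bound gives 53.6%, 40.4% and 31.9% at 0%, 2% and 5% improvers.

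If the exact binomial interval is retained instead, 16.5 should say that it is one-sided and how it is applied to a net count. Section 16.42 should then give a distance of 4.9 points at 15/153, a largest passing net count of 14/153, and a 42.8% chance of passing at a true 10% with no improvers.

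The cost is revised wording in 16.42 and 16.5 and a short recalculation, with no extra patients. The stated precision and chance of success will look less favourable than they do now.

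### The operating characteristics in 16.42 do not follow from n=153 and the 14% rule: a true 15% increase would pass about 2–4% of the time, not 48.6%

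*Combined protocol and SAP*

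**What the plan says.** Section 16.41 sets the size: "This study requires 153 evaluable women for the primary endpoint analysis". Section 16.42 gives the basis. "A one-sided 95% confidence interval (with the upper bound of the interval) was computed", taking the increase as "3 years compared to baseline is 10%, and the distance from 10% to the upper bound of the CI is 4" percentage points. The go decision reads: "If the upper bound of the one-sided CI for the difference of adverse cosmesis rate lies below 14%, then recommend further investigation".

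The plan then ties its probabilities to that design: "The table below shows the operating characteristics of this trial with 153 patients and the decision rule given above". The table lists 98.4%, 72.8%, 48.6% and 29.8% for true increases of 5%, 10%, 15% and 20%. The paragraph after it repeats 98.4% for 5% and continues: "this drops to 72.8% if the true rate is 10%, and further drops to 49.6% if the true rate is 15" percent. Table and text therefore differ at 15% (48.6% against 49.6%).

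Section 16.5 builds the estimator from a net count, "number of women who had an adverse cosmesis event at 3 years minus number of women who had an adverse cosmesis event at baseline". It expresses this as a share of everyone analysed and attaches an exact binomial interval at the 95% level. It applies the same 14% limit but does not repeat that the interval is one-sided. Section 16.42 says one-sided but names no interval method.

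**The concern.** The table can be doubted without software. The trial is sized so that an observed increase of 10% has an upper bound of 14%, so the rule passes only when the observed increase is about 10% or less. A true increase of 10% should then pass roughly half the time, not 72.8%. An upper bound with true one-sided 95% coverage falls below 14% at most about 5% of the time when the truth is 14% or more. Pass rates of 48.6% at 15% and 29.8% at 20% cannot come from such a rule.

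This table and its paragraph are the only place where the plan states how often its primary go/no-go rule reaches each decision. A sponsor, IRB or monitoring board reading it would believe two things: that a regimen performing at the planning value has nearly three chances in four of success, and that one worse than the plan's own limit has about an even chance of being recommended.

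**Working it through.** **Inputs.** n=153; one-sided 95% bound (z=1.645); planning value 10%; distance to the bound 4 points; limit 14% (all 16.41–16.42). The estimator and the exact binomial interval come from 16.5.

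**Step 1: the sample size.** n = (1.645/0.04)² × 0.10 × 0.90 = 152.2, rounded up to 153. The stated size reproduces with a one-sided normal bound on one binomial proportion. A two-sided interval would have needed (1.96/0.04)² × 0.09 = 216.1, so 217.

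**Step 2: the largest count that passes.** Let x be the net number of adverse events out of 153.

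- Exact one-sided bound (95th percentile of Beta(x+1, 153−x)): x=14 gives 13.93%, pass; x=15 gives 14.69%, fail.
- Normal one-sided bound (x/n + 1.645·√[(x/n)(1−x/n)/n]): x=15 gives 0.0980 + 1.645 × 0.0240 = 13.76%, pass; x=16 gives 14.53%, fail.
- Exact two-sided 95% interval, should 16.5 mean that: x=12 gives 13.30%, pass; x=13 gives 14.09%, fail.

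**Step 3: pass probability**, P(X ≤ cut-off) with X ~ Binomial(153, p).

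| True increase | Plan | Exact one-sided (≤14) | Normal one-sided (≤15) | Exact two-sided (≤12) |
|---|---|---|---|---|
| 5% | 98.4% | 99.0% | 99.6% | 95.6% |
| 10% | 72.8% | 42.8% | 53.6% | 23.0% |
| 14% | not given | 4.8% | 7.9% | 1.4% |
| 15% | 48.6% (text 49.6%) | 2.3% | 4.0% | 0.6% |
| 20% | 29.8% | 0.02% | 0.05% | <0.01% |

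**Step 4: could some other cut-off explain the table?** At n=153 the nearest cut-off for each row is 14 events for 5% (99.0%), 17 for 10% (73.1%), 22 for 15% (47.0%) and 27 for 20% (27.0%). The rows do not share one rule. The best single cut-off, 22, gives 100.0/96.9/47.0/4.7% and misses the 20% row by 29.8 − 4.7 = 25.1 points. A search over every sample size below 300 found no exact match. The closest was n=17 with cut-off 2, still 3.4 points off.

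**Step 5: does the net-count estimator matter?** The 16.5 estimator is worsened minus improved, so its spread depends on the share of women, i, who move out of fair or poor cosmesis. The documents give no such share; 2–20% is assumed here. Each woman scores +1 with probability d+i, −1 with probability i, and 0 otherwise, where d is the true net increase. Scores are summed over 153 women.

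| True increase | Exact cut-off (≤14) on net count | Normal cut-off (≤15) on net count | Paired Wald one-sided bound |
|---|---|---|---|
| 5% | 80–97% | 83–98% | 51–97% |
| 10% | 44–46% | 51–52% | 18–40% |
| 14% | 8–22% | 11–25% | 5–6% |
| 15% | 4–17% | 7–20% | 3.2–3.5% |
| 20% | 0.1–4% | 0.2–5% | 0.1–0.4% |

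The paired bound is D + 1.645·√[(b + c − (b−c)²/n)/n²], with b women worsened, c improved and D=(b−c)/n. Across the upper-bound calculations in Steps 3 and 5, the highest values are 53.6% at 10%, 20.3% at 15% and 5.2% at 20%, all well short of the table.

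**The case against.** The strongest reply is that nothing in the trial's result depends on the table. The decision uses the observed confidence interval, n=153 is derived without the table, and safety stopping has its own rules in 16.92. At 15% and 20% the error is also cautious, since it shows the rule accepting a poor regimen more often than it would. All of this is true and limits the harm to how the design is understood and approved. It does not make the figures right, and at 10% the error is in the optimistic direction.

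A second reply is that the interval is adequately specified: 16.42 supplies the side, 16.5 supplies the method and refers back, and together they mean an exact one-sided bound. That is the natural joint reading, and under it the replacement figures are 99.0/42.8/2.3/0.02%. But the sample size was reached with the normal formula and 16.5 is silent on sidedness, so other readings remain open, and they change decisions. With 15 of 153 the normal bound passes and the exact one fails. With 13 or 14 the exact one-sided bound passes and the exact two-sided one fails.

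Third, a 20% improvement share exceeds the only baseline rate of fair or poor cosmesis that the documents give for an APBI arm (19%, from the external trial cited in 1.3.2), and no more women can improve than start out adverse. This is fair. Capping the share at 19% in the same calculation lowers the maxima only to 19.9% at 15% and 4.9% at 20%. The conclusion does not need this assumption.

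**Conclusion.** The concern holds. Three of the four rows do not follow from the stated sample size and rule. Under the plan's single-binomial model with a one-sided 95% bound, the 10% row is too high by 19 to 30 points (72.8 against 53.6 or 42.8), the 15% row by about 45 to 46 points (48.6 against 4.0 or 2.3), and the 20% row by almost its full 29.8 points. The 5% row is close under that model. The 48.6%/49.6% disagreement is a separate, smaller inconsistency.

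The exact replacement figures depend on the interval method, its sidedness and, because the estimator is a net change, the share of women who improve. The finding that the table is wrong depends on none of these. The sample size is consistent with its stated inputs.

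**What to change.** 1. Name one interval method and one sidedness, in the same words, in 16.42 and 16.5.
2. State the assumed share of women who improve from fair or poor cosmesis and how the interval allows for it.
3. Recompute the table and the paragraph after it for that method at n=153, so that they agree. If the exact one-sided bound with no improvement is kept, the rows become 99.0%, 42.8%, 2.3% and 0.02%.
4. Add a row at 14% giving the false-acceptance probability. On the single-binomial model it is 4.8% (exact one-sided), 7.9% (normal one-sided) or 1.4% (exact two-sided). It is higher if a single-binomial cut-off is applied to a net count that includes improvers.

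The cost is a short recalculation and matching wording, settled before outcome data are examined. Correcting the text needs no extra patients and no change to the 14% limit. A sponsor who relied on 72.8% at the planning value may, however, wish to reconsider the size once it sees a figure nearer 43–54%, or lower under a two-sided or paired interval.
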